10.1.2. Laboratory Assessments

Haematology and clinical chemistry values will be listed by subject and time point including changes from baseline and repeat/unscheduled measurements. Summary tabulations including absolute value and changes from baseline will be presented by treatment and time point for the safety analysis set. The baseline for the measurements will be the last measurement prior to dosing in the respective treatment periods. When a value is not available prior to treatment, the screening value will be taken as baseline. Changes from baseline will be calculated and presented for all post-baseline time points including the Follow-up Visit. Shift tables will also be presented for certain parameters.

A summary of the key subject information on the laboratory changes outside the predefined criteria will also be presented.

Any laboratory parameters with results from the laboratory given as “< xx” or “>xx” in the database will be imputed with the absolute value of the number without the sign (eg, < 2.2 will be imputed as 2.2) for the descriptive statistics and changes from baseline.

The listings will include the following information: test name, date of measurement, reference range, result and flags for any measurements that are outside the reference range (eg,

AstraZeneca, program, or laboratory ranges). Clinical laboratory data will be reported in System International units in the CSR.

Additional listings will be presented for the following:

- Urinalysis (macroscopic and microscopic, if applicable).
- FSH.

The results of viral serology (including SARS-CoV-2 serology), SARS-CoV-2 RT PCR, and the drugs of abuse and alcohol screen will not be listed in the CSR.

Lastly, a summary describing subjects with potential Hy's Law results will be presented by subject and time point. Parameters might include ALT, AST, total bilirubin and ALP.

10.1.3. Physical Examination

The baseline/screening results of the physical examination will be documented in medical history for each subject.

Any new or aggravated clinically relevant abnormal medical physical examination finding compared to the baseline assessment will be reported as an AE.

10.1.4. Resting 12-lead Electrocardiogram

Results of the safety ECGs (normal/abnormal assessments and specific findings) will be listed for each subject.

Electrocardiogram parameter results will also be listed by treatment for each subject and time point of PR, RR, QRS, QT interval and the derived values of QTcF and HR. All parameters will have changes from baseline derived and presented.

The following ECG parameters will be derived:

- QTcF will be calculated as $QTcF = QT * RR^{-1/3}$ where the QT interval is in milliseconds and the RR interval is in seconds
- HR will be calculated, based on the RR interval as $HR = 60/RR$ interval, where the RR interval is in seconds

Descriptive statistics will be presented by treatment and time-point for the original and changes from baseline values of PR, RR, QRS, QT; derived values and changes from baseline for QTcF and HR will also be included. The baseline for the ECG measurements will be the pre-dose assessment on Day 1.

Outliers with respect to QTcF will also be tabulated for the following categories:

- Absolute value > 450 ms and ≤ 480 ms.
- Absolute value > 480 ms and ≤ 500 ms.
- Absolute value > 500 ms.
- Increase from baseline > 30 ms and ≤ 60 ms.
- Increase from baseline > 60 ms.

All calculations of ECG parameters and reporting described in this section will be performed by Parexel.

10.1.5. Vital Signs

The results of the vital signs measurements will be listed by subject and time point including the date/time of the assessment, changes from baseline and repeat/unscheduled measurements. The baseline for vital signs measurements will be last measurement prior to dosing in the respective treatment periods. Descriptive statistics will be presented by treatment and time point for both observed values and changes from baseline.

10.2. Pharmacokinetics

10.2.1. Whole Blood Pharmacokinetic Parameters

The following PK parameters will be determined where possible from the whole blood concentrations of tacrolimus/cyclosporin.

Primary PK parameters

AUC _{inf}	Area under concentration-time curve from time zero to infinity
AUC _{last}	Area under the concentration-time curve from time zero to time of last quantifiable concentration
C _{max}	Maximum observed concentration

Secondary PK parameters

t _{max}	Time to reach maximum observed concentration following drug administration
t _{1/2λz}	Half-life associated with terminal slope (λ _z) of a semi-logarithmic concentration-time curve
CL/F	Apparent total body clearance of drug after extravascular administration
V _z /F	Apparent volume of distribution during the terminal phase after extravascular administration

The following diagnostic parameters will also be determined:

λ_z	Terminal elimination rate constant
λ_z lower	Lower (earlier) t used for λ_z determination
λ_z upper	Upper (later) t used for λ_z determination
λ_z, N	Number of data points used for λ_z determination
λ_z span ratio	Time period over which λ_z was determined as ratio of $t^{1/2}/\lambda_z$
Rsq adj	Statistical measure of fit for the regression used for λ_z determination adjusted for the number of used data points (n obs)
AUCextr	Extrapolated area under the curve from tlast to infinity, expressed as percentage of AUCinf

Additional PK parameters may be determined where appropriate.

10.2.2. Calculation or Derivation of Pharmacokinetic Parameters

The PK analyses of the whole blood concentration data for tacrolimus/cyclosporin will be performed by Covance, on behalf of AstraZeneca, according to the AstraZeneca standards (LDMS_001_00201968 dated 13 July 2020).

PK parameters will be derived using non-compartmental methods with Phoenix[®] WinNonlin[®] Version 8.1, or higher.

Pharmacokinetic analysis will, where possible, be carried out using actual times recorded in the raw data. If actual times are missing, nominal times will be used.

Concentration data will be used as supplied by the analytical laboratory for PK analysis. The units of concentration and resulting PK parameters, with the amount and concentration units, will be presented as they are received from the analytical laboratory unless otherwise specified on the PK order form.

The Cmax and tmax will be derived directly from the plasma concentration-time profiles. For multiples peaks the highest post-dose concentration will be reported as Cmax. In the case that the multiple peaks are of equal magnitude, the earliest tmax will be reported.

Plasma concentrations which are BLQ prior to the administration of the first dose and up to the quantifiable concentration will be set to a value of zero with the following exceptions:

- After the first quantifiable concentration, any BLQ concentrations will be set to missing for all concentration profiles.
- Where 2 or more consecutive concentrations are BLQ at the end of a profile, the profile will be deemed to have terminated and therefore any further quantifiable concentrations

will be set to missing for the calculation of the PK parameters unless it is considered to be a true characteristic of the profile of the drug.

- Any embedded BLQ value (between 2 quantifiable concentrations) will be set to missing for the purposes of PK analysis.
- If an entire concentration-time profile is BLQ, the profile will be excluded from the PK analysis.

Terminal elimination half-life, calculated as $(\ln 2)/\lambda_z$, will be estimated by log-linear least-squares regression of the terminal part of the concentration-time curve. For the determination of λ_z , the start of the terminal elimination phase for each subject will be defined by visual inspection and will be the first point observed after C_{max} at which there is no systematic deviation from the log-linear decline in plasma concentrations. A minimum of 3 data points will be used in calculating λ_z , and the duration of time over which λ_z is recommended to be at least 3 times the subsequently estimated terminal half-life. Where an elimination half-life is estimated over less than 3 times the subsequently estimated terminal half-life, the robustness of the data will be discussed in the study report. The adjusted correlation coefficient (R_{sq_adj}) should be ≥ 0.8 . Where $R_{sq_adj} < 0.8$, $t_{1/2\lambda_z}$ and related parameters will be listed, flagged and excluded from descriptive and inferential statistics.

AUC_{inf} is estimated by $AUC_{last} + C_{last}/\lambda_z$ where C_{last} is the observed last quantifiable drug concentration.

AUCs (including AUC_{inf} and AUC_{last}) will be calculated using the linear trapezoidal method when concentrations are increasing and the logarithmic trapezoidal method when concentrations are decreasing (linear up log down).

The minimum requirement for the calculation of AUC will be the inclusion of at least 3 consecutive plasma concentrations above the LLOQ, with at least 1 of these concentrations following C_{max} .

If AUC_{inf} cannot be determined for all subjects or all dose levels, an alternative AUC measure, such as AUC to a fixed time point, may be used in the evaluation of DDI.

If the concentration at the time of dosing is missing, then this will be set to 0.

Pharmacokinetic parameters associated with positive pre-dose value(s) of greater than 5% C_{max} may be excluded from the summary statistics of PK tables and statistical analysis at the discretion of the pharmacokineticist.

11. STATISTICAL METHODS AND SAMPLE SIZE DETERMINATION

11.1. Description of the Analysis Sets

11.1.1. Safety Analysis Set

The safety analysis set will include all subjects who received at least 1 dose of tacrolimus (Cohort 1) or cyclosporin (Cohort 2) and for whom any safety post-dose data are available.

Unless otherwise stated, the randomised set will be used for the presentation of all demographic and disposition data, and the safety analysis set will be used for all safety analyses. Exposure to IMP will also be presented using the safety analysis set.

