5.4.3. Dose and Treatment Regimens

Each subject will receive single oral doses of SZC and/or tacrolimus/cyclosporin under fasted conditions. The doses will be administered after an overnight fast of at least 12 hours.

Sodium zirconium cyclosilicate will be administered orally as suspension, containing **CCI** of IMP dissolved in 45 mL of water. Tacrolimus and cyclosporin will be administered as oral capsules for swallowing with 200 mL of non-carbonated water at room temperature.

On days of IMP co-administration, SZC will be administered immediately followed by tacrolimus/cyclosporin.

Subjects will be allowed to drink water to prevent dehydration until 1 hour before dosing. Water will be allowed ad libitum from 2 hours after dosing and a standard meal will be given 4 hours after dosing.

After dosing, subjects will remain semi-supine on their bed or sitting (except when necessary for study procedures) until 4 hours after dosing.

Other restrictions, including posture control are described in Section 4.2. Data of subjects may be excluded from the PK analysis set as described in Section 11.1.2.

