6.3.1.4. Recording of Adverse Events

Time Period for Collection of Adverse Events

Non-serious AEs will be collected from administration of IMP in Treatment Period 1 throughout the treatment period and including the Follow-up Visit.

Serious AEs will be recorded from the time of informed consent.

Follow-up of Unresolved Adverse Events

Any AEs that are unresolved at the subject's last visit in the study are followed up by the Investigator for as long as medically indicated, but without further recording in ClinBase™.

AstraZeneca retains the right to request additional information for any subject with ongoing AE(s)/SAE(s) at the end of the study, if judged necessary.

Variables

The following variables will be collected for each AE:

- AE diagnosis/description.
- The date and time (if known) when the AE started and stopped.
- Maximum intensity.
- Whether the AE is serious or not.
- Investigator causality rating against the IMPs (yes or no).
- Action taken with regard to IMP.
- Outcome.

In addition, the following variables will be collected for SAEs:

- Date AE met criteria for SAE.
- Date Investigator became aware of SAE.
- AE is serious due to.
- Date of hospitalisation.
- Date of discharge.
- Probable cause of death.
- Date of death.

- Autopsy performed.
- Causality assessment in relation to study procedure(s).
- Causality assessment to other medication.

The following intensity ratings will be used:

- 1 Mild (awareness of sign or symptom, but easily tolerated).
- 2 Moderate (discomfort sufficient to cause interference with normal activities).
- 3 Severe (incapacitating, with inability to perform normal activities).

It is important to distinguish between serious and severe AEs:

- Severity is a measure of intensity whereas seriousness is defined by the criteria in Section 6.3.1.2.
- An AE of severe intensity need not necessarily be considered serious. For example, nausea that persists for several hours may be considered severe nausea, but not an SAE. On the other hand, a stroke that results in only a limited degree of disability may be considered a mild stroke but would be an SAE.

Causality Collection

The Investigator will assess causal relationship between IMPs and each AE, and answer “yes” or “no” to the question “Do you consider that there is a reasonable possibility that the event may have been caused by the IMP?”

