11.2. Methods of Statistical Analyses

11.2.1. General Principles

The statistical methodology below describes the statistical analysis as it is foreseen when the study is being planned.

If circumstances should arise during the study rendering the analysis inappropriate, or if in the meantime improved methods of analysis should come to light, different analyses may be performed. A separate SAP will not be written for the study. Any deviations from the statistical methodology defined in this protocol, reasons for such deviations and all alternative/additional statistical analyses that may be performed will be described in the CSR.

Such changes to analyses may be written into an abbreviated SAP, if appropriate. The verification and review of all statistical modelling assumptions will be documented appropriately.

All analyses discussed below will be replicated for both of the cohorts.

Data listings will be based upon the safety analysis set. All original and derived PK parameters will be summarised using the PK set. Demographic and disposition data will be summarised, using the safety set. Safety data will be summarised using the safety set.

All summaries done "by treatment" will be performed by actual treatment, rather than treatment to which a subject was randomised.

For each cohort, demographic and baseline data will be summarised for all subjects in the randomised, by sequence and overall. Pharmacokinetic data will be summarised by treatment, or treatment and time point, as appropriate. Adverse events will be presented by treatment and overall. Safety data collected at multiple occasions within the same period will be presented by treatment, time point and overall.

Frequency counts (number of subjects [n] and percentages) will be made for categorical variables. Descriptive statistics (n, mean, SD, median, minimum and maximum) will be calculated for continuous variables. Descriptive statistics will only be presented if $n \geq 3$. If no subjects have data at a given time point, then only $n = 0$ will be presented. If $n < 3$, only the n, minimum and maximum will be presented. The other descriptive statistics will be left blank.

The following rules will apply to any repeated safety assessments occurring within each treatment period:

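### The safety analysis set ignores SZC doses, so a subject who takes SZC in Period 1 but never the capsule falls outside it; Section 11.2.1 also puts demographics and disposition on the wrong set

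*Protocol*

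**What the plan says.** Section 11.1.1 defines the safety analysis set as "all subjects who received at least 1 dose of tacrolimus (Cohort 1) or cyclosporin (Cohort 2"), with the further condition that some safety data after dosing exist. It then states that "the safety analysis set will be used for all safety analyses" and that "Exposure to IMP will also be presented using the safety analysis set". Section 11.2.1 bases the data listings on the same set and organises by-treatment summaries by the treatment actually received.

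SZC is one of the three IMPs (Section 5.4.1, Table 5; Section 5.4.2). For co-administration days, Section 5.4.3 gives the order: "SZC will be administered immediately followed by tacrolimus/cyclosporin". Under the footnotes to Table 3, sequences BA and DC have SZC in Treatment Period 1. On adverse events, Section 6.3.1.4 says: "Non-serious AEs will be collected from administration of IMP in Treatment Period 1".

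On a second matter, Section 11.1.1 says "the randomised set will be used for the presentation of all demographic and disposition data", while Section 11.2.1 says "Demographic and disposition data will be summarised, using the safety set".

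**The concern.** Entry to the safety set depends on the second of two products taken in succession, while adverse event collection starts with the first. In sequences BA and DC a subject may take SZC in Period 1, stop before the capsule and not return. That subject has received an IMP and may have a recorded event, but does not qualify for the set.

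The exclusion is also one-sided. It can act only after SZC intake, and SZC is the product whose co-administration the secondary safety objective examines (Section 2.2). No corresponding exclusion exists for tacrolimus or cyclosporin given alone, because taking the capsule is itself the entry condition.

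The wording matters more than usual because Section 11.2.1 states that no separate SAP will be written and allows at most an abbreviated one for changes. The protocol text is therefore the working analysis plan. The same applies to the conflict over which set carries demographics and disposition.

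**Working it through.** **Who can be affected.** Section 5.1.1 plans 15 subjects in each of four sequences: 4 × 15 = 60, which reproduces the stated total.

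- AB and CD subjects take tacrolimus or cyclosporin alone in Period 1. Once they have done so they are eligible for the set, whatever happens in Period 2.
- BA and DC subjects take SZC first in Period 1, before any capsule. That is 15 subjects in Cohort 1 and 15 in Cohort 2, or 2 × 15 = 30 across the study.

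**How likely a case is.** The protocol gives no rate for SZC taken without the capsule. For an assumed per-subject probability p, the chance of at least one case among n subjects is 1 − (1 − p)^n. The three rates below are assumptions chosen to show a range.

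| Assumed p | One cohort, n = 15 | Both cohorts, n = 30 |
|---|---|---|
| 0.1% | 1 − 0.999^15 = 1.5% | 1 − 0.999^30 = 3.0% |
| 1% | 1 − 0.99^15 = 14.0% | 1 − 0.99^30 = 26.0% |
| 3% | 1 − 0.97^15 = 36.7% | 1 − 0.97^30 = 59.9% |

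**Where the subject's data would go.**

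| Section | What it implies for an SZC-only subject |
|---|---|
| 11.1.1 | Outside the set for all safety analyses and IMP exposure |
| 11.2.1 | Outside the listings, which rest on the safety set |
| 11.2.5 | Safety variables are analysed on the safety set (out), but all safety data are to be listed (in) |
| 10.1.1 | AEs are listed for each subject, and AEs after Period 1 dosing are summarised for all subjects (in) |
| 11.2.2 | Every subject is to be included in the safety analyses to the extent the data allow (in) |
| 6.3.1.5 | All SAEs are recorded and reported regardless of analysis set (in) |
| 11.2.3 | Disposition and discontinuation reasons cover everyone randomised (in) |

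Sections 10.1.1, 11.2.2 and 11.2.5 pull towards inclusion, but none redefines the set. Section 11.2.5 also reports SAEs before dosing separately. That does not clearly cover an event after SZC and before the capsule, and it does not cover non-serious events.

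**Which treatment column.** Section 3.1 defines treatments A to D, and none is SZC alone. With summaries by actual treatment, an SZC-only exposure has no column. This also applies to an AB or CD subject who takes only SZC in Period 2.

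**Demographics and disposition.** Section 11.1.1 assigns both to the randomised set. Section 11.2.3 presents disposition on all randomised subjects, Section 11.2.3.1 uses randomised subjects as the denominator for demographics, and a later paragraph of Section 11.2.1 uses them for demographic and baseline data. One sentence in Section 11.2.1 says otherwise. The proviso in Section 11.1.1 that allows exceptions cannot reconcile that sentence with Sections 11.2.3 and 11.2.3.1.

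**PK.** Section 11.1.2 separately requires a quantifiable post-dose tacrolimus or cyclosporin concentration. Widening the safety set by SZC-only subjects leaves the PK analysis set unchanged.

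**The case against.** The strongest reply is that the gap is very narrow. Both products are scheduled at 0 h on Day 1 (Table 3), the capsule follows SZC at once, and dosing is directly supervised (Section 5.6). Anyone who reacts or vomits after swallowing the capsule remains eligible for the safety set. A reader might infer that the definition removes subjects with SZC intolerance in general. It does not: it reaches only those who stop between two consecutive doses, in Period 1, in two of the four sequences.

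A reader might also infer that the event would be lost altogether. The documents do not support that. SAE reporting and disposition stand outside the safety set, the text on listings points both ways, and Section 11.3 has a data review meeting before database lock at which the analysis sets are settled. What most clearly follows from the definition is absence from the by-treatment summaries and the exposure presentation.

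Nor can a number of affected subjects be stated, since no rate is given, or each event called SZC-related, since causality is for the investigator (Section 6.3.1.4). The 30 BA and DC subjects are not the denominator of any planned table, because analyses run by cohort. An SZC-only subject also received neither arm of the comparison in the secondary objective, so counting that subject as co-administered would be wrong in the other direction. Finally, nothing here argues against requiring post-dose safety data.

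These objections stand and keep the point minor. They do not remove the mismatch between an entry rule that ignores one IMP and collection rules that include it. Similarly, Section 11.2.3 already protects disposition from hiding undosed subjects, so the second matter is a plain contradiction with little analytic consequence.

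**Conclusion.** The point holds as a minor defect in two stated rules.

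First, the safety set is defined by tacrolimus or cyclosporin only. A BA or DC subject with SZC alone in Period 1 would be left out of the by-treatment safety summaries and IMP exposure and, on the wording of Section 11.2.1, the listings. Sections 10.1.1, 11.2.2 and 11.2.5 conflict with that result. The affected group is at most 15 subjects per cohort. The expected number is unknown but should be small; the probabilities shown rest wholly on assumed rates.

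Second, Section 11.2.1 contradicts Sections 11.1.1, 11.2.3 and 11.2.3.1, and its own later paragraph, on the set for demographics and disposition. This needs no hypothetical case.

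No PK result or conclusion on the interaction is affected.

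**What to change.** 1. In Section 11.1.1, define the safety analysis set as all subjects with at least one dose of any IMP (SZC, tacrolimus or cyclosporin) and any post-dose safety data.
2. Add a rule that an SZC-only exposure, in either period, is shown separately or with a footnote and is not counted as completed co-administration.
3. Align Sections 10.1.1, 11.2.1, 11.2.2 and 11.2.5 with the new definition, so that summaries and listings rest on the same stated population.
4. Delete the sentence in Section 11.2.1 that places demographic and disposition data on the safety set.

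The cost is protocol wording and, if a case occurs, one footnote or extra row in the tables. Sample size, data collection and the PK analysis do not change.
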